11. DATA COLLECTION AND QUALITY ASSURANCE

11.1. Data Collection Methods

Data for each subject at each site will be entered into an electronic data capture (EDC) system. Paper forms used as CRFs, during enrollment, or at other time points will be entered into

the EDC by site staff. Surveys are administered to subjects to collect baseline, follow-up, AE/SAE, user feedback, and exit data. Subjects use their own devices to complete these surveys and Diaries online. Forms will record the subject's ID, assigned site, date completed, and other relevant information. Subjects will be trained during or after enrollment on how to use and fill out these surveys. Support and re-training will be provided to subjects whenever requested.

Appropriate security and privacy settings in the EDC system, or procedures set up for use with the EDC system, will be put in place to meet minimum applicable regulations. These may include audit trails, unique log-ins, and custom user access. The EDC system will be set up and managed by the sponsor's Clinical Trials Manager or Clinical Trials Data Manager. Before study launch, the system will be tested and validated.

11.2. Data Management

The Sponsor Clinical Research (Data) Manager will control access to the EDC. Specific forms and functions will be granted to Sponsor and site staff based on their role in the study. The Clinical Research (Data) Manager will create the surveys and electronic workflow.

Site staff and the Clinical Research Manager will have access to subject responses in the EDC and will have the ability to correct data when necessary. Data correction may occur in instances where a subject enters the wrong information (e.g., puts in 2018 for their birth year) and the correction has been verified.

Once data collection is complete, the Clinical Research (Data) Manager will work with site staff to ensure accuracy and completeness of the data. Data will be exported, reviewed, cleaned as necessary, and then locked for statistical analysis.

Unlocking of the database requires justification and approval. Reasons for unlocking, date of unlocking, and date of re-locking the database will be documented.

11.3. Quality Assurance

11.3.1. Training

Training on the protocol, procedures, forms, and EDC system will be provided to the site prior to launch of the study. Training may be completed through teleconference or in-person, as determined between the Sponsor and the site. Training will be documented in Training logs.

11.3.2. Deviations/Violations

A deviation is an unplanned departure from protocol by the staff, participant, or investigator that does not cause significant consequences and is not intended to be a permanent or systematic change.

A violation is a divergence from protocol that reduces the quality or completeness of the data (e.g., missing or erroneous critical information on the surveys, I/E criteria not met), makes the Informed Consent Form inaccurate (e.g., ICF not fully signed), or impacts a subject's safety, rights, or welfare (e.g., unreported SAEs). Other violations include repeated subject non-compliance and intentional departures from protocol.

Site staff and PIs should be vigilant in identifying, recording, and addressing all deviations from and violations of the protocol. All deviations and violations should be recorded in the Deviations/Violations Log. The PI or appropriately delegated individual will determine if the Sponsor and/or IRB should be notified. Any deviation or violation performed to protect patient safety or confidentiality or otherwise impacting patient safety or confidentiality should be immediately reported to the IRB and Sponsor.

11.3.3. Monitoring

A staff member(s) at each site will be responsible for regularly monitoring subject responses in the EDC system. If a subject misses Diary entries or survey responses beyond the acceptable windows, the designated site staff member will contact subject to ensure completion of the documents.

The site staff member will also follow up with subjects to clarify entries that are or seem to be incorrect or questionable.

The Sponsor Clinical Trials Manager or Data Manager will similarly monitor subject compliance and safety across all sites weekly or biweekly. Any errors, discrepancies, missed entries, or other entries of concern will be queried to the respective site. The clinical research coordinators (CRC) or similarly designated staff member at each site is expected to respond to and resolve or help the Manager resolve the issue in a timely manner. Queries and resolution will be tracked by the Clinical Trials Manager.

The Clinical Trials Manager (or similarly designated staff member) will also check in regularly with each site to review items such as enrollment status, subject compliance and safety, supplies, and site questions or issues. These will be tracked in a Remote Monitoring Log.

After the first 3 subjects are enrolled at each site, the Clinical Trials Manager or Associate will check in with the site to ensure procedures are being conducted as expected and to address any problems early on. If refresher training is needed, the site may request virtual in-person training with the Clinical Trials Manager.

Interim monitoring visit(s) may be scheduled as needed.

11.4. Study Data & Records Retention

Study records will be maintained for at least 2 years after study close-out.

12. PARTICIPANT RIGHTS AND CONFIDENTIALITY

12.1. Institutional Review Board (IRB)

This protocol and the informed consent document (provided as a separate document) and any subsequent modifications will be reviewed and approved by the IRB or ethics committee responsible for oversight of the study.

12.2. Informed Consent Forms

The most recently approved version of the Informed Consent Form (ICF) will be used to obtain and document informed consent of study participants. The ICF is provided in English with no translations planned. If a new version of the ICF is approved during the study, previously consented and enrolled subjects will be re-consented using the newly approved ICF, only if the changes to the ICF are substantial and the IRB requires re-consent.

A signed ICF will be obtained from each participant. For participants who cannot consent for themselves, such as those with a legal guardian, the guardian must sign the ICF. The ICF will describe the purpose of the study, the procedures involved, the requirements to follow, the risks and benefits of participation, and compensation. A copy will be given to each participant or legal guardian.

12.3. Participant Confidentiality

During screening, prospective subjects agree to provide their name, email, phone number, and potentially general area of residence (such as zip code, for assignment to closest research site). This information is used to email the prospect introductory study information and send study surveys and forms. To protect the privacy of enrolled subjects, no personally identifiable information will be included in any material sent to the Sponsor (except in cases listed below). This includes: enrollment logs, patient names, phone numbers, fax numbers, patient addresses, Social Security numbers, local hospital medical record number.

The Sponsor employee responsible for shipping devices to enrolled subjects (“Shipping Associate”) will be not be involved in any other clinical research and will only receive the minimum necessary information to ship the correct devices to the subject (i.e., name, address, treatment).

Compensation also requires that the name and address of the subject be provided to a Sponsor employee handling finances. In these cases, the name and address of the subject without the associated Subject ID will be sent to the designated employee to process and send compensation. The shipping and compensation employees will not be involved with any other component of the study and will not share any subject’s personally identifiable information with Sponsor employees associated with the study.

13. PUBLICATION OF RESEARCH

Authorship will reflect joint cooperation between PPS and participating PI(s). Authorship responsibilities should be established prior to the writing of any manuscript.

No individual publications are allowed unless agreed upon, reviewed, and approved by the Sponsor before submission and/or publication. No individual publications are allowed prior to the completion of a final report for the study.

14. ABBREVIATIONS

AE	Adverse Event
BCTQ	Boston Carpal Tunnel Questionnaire
CFR	Code of Federal Regulations
CRA	Clinical research associate
CRC	Clinical research coordinator
CRF	Case report form
CTR	Carpal tunnel release
CTS	Carpal tunnel syndrome
EDC	Electronic data capture (usually followed by “system”)
FDA	(U.S.) Food and Drug Administration
FSS	Functional Severity Scale (of the BCTQ)
HIPAA	Health Insurance Portability and Accountability Act
ICF	Informed Consent Form
IRB/IEC	Institutional Review Board / Independent Ethics Committee
NCS	Nerve conduction study
NIBIB	National Institute of Biomedical Imaging and Bioengineering
NIH	National Institute of Health
NPRS	Numeric Pain Rating Scale
NSAID	Non-steroidal anti-inflammatory drug
PPS	Pressure Profile Systems, Inc. (Sponsor)
SAE	Serious Adverse Event
SAP	Statistical Analysis Plan
SSS	Symptom Severity Scale (of the BCTQ)
Survey	Various questionnaires completed by patients and used to collect study data (includes Follow-up and User Feedback Surveys)

Appendix I: Boston Carpal Tunnel Questionnaire (BCTQ)

Appendix II: Nerve Conduction Study (NCS)

APPENDIX I: BOSTON CARPAL TUNNEL QUESTIONNAIRE (BCTQ)

The Boston Carpal Tunnel Questionnaire (BCTQ) is a patient-administered measure of symptom severity and functional impairment due to carpal tunnel syndrome. It has been shown to be “valid, reliable, responsive, and acceptable” tool to use as a primary outcome measure in carpal tunnel syndrome studies¹³.

Each response has a value from 1 to 5. The average value of the responses to the first 11 questions provides the Symptom Severity Scale (SSS) score. The average value of the responses to the remaining 7 questions provides the Functional Severity Scale (FSS) score. The lowest value is 1 and represents no symptoms or functional impairment. The highest value is 5 and represents the worst possible symptoms and functional impairment.

Boston Carpal Tunnel Questionnaire (BCTQ)

The BCTQ is 2-part survey that quantifies the severity of your carpal tunnel syndrome. Thinking about your symptoms due to carpal tunnel syndrome for **a typical twenty-four (24) hour day during the past two (2) weeks**, please answer the following questions. (If you have bilateral CTS (both hands affected), answer for the wrist that is more severe based on the nerve conduction study (NCS) results. If difficult to tell, answer for your dominant hand.)

Part I - Symptom Severity Scale (SSS)

1. **How severe is the hand or wrist pain that you have at night?**
 - I do not have hand or wrist pain at night
 - Mild pain
 - Moderate pain
 - Severe pain
 - Very severe pain

2. **How often did hand or wrist pain wake you up during a typical night in the past two weeks?**
 - Never
 - Once
 - Two or three times
 - Four or five times
 - More than five times

3. **Do you typically have pain in your hand or wrist during the daytime?**
 - I never have pain during the day
 - I have mild pain during the day
 - I have moderate pain during the day
 - I have severe pain during the day
 - I have very severe pain during the day

4. **How often do you have hand or wrist pain during the daytime?**
 - Never
 - Once or twice a day
 - Three to five times a day
 - More than five times a day

-
- The pain is constant
5. **How long, on average, does an episode of pain last during the daytime?**
- I never get pain during the day
- Less than 10 minutes
- 10 to 60 minutes
- Greater than 60 minutes
- The pain is constant throughout the day
6. **Do you have numbness (loss of sensation) in your hand?**
- No
- I have mild numbness
- I have moderate numbness
- I have severe numbness
- I have very severe numbness
7. **Do you have weakness in your hand or wrist?**
- No weakness
- Mild weakness
- Moderate weakness
- Severe weakness
- Very severe weakness
8. **Do you have tingling sensations in your hand?**
- No tingling
- Mild tingling
- Moderate tingling
- Severe tingling
- Very severe tingling
9. **How severe is numbness (loss of sensation) or tingling at night?**
- I have no numbness or tingling at night
- Mild
- Moderate
- Severe
- Very severe
10. **How often did hand numbness or tingling wake you up during a typical night during the last two weeks?**
- Never
- Once
- Two or three times
- Four or five times
- More than five times
11. **Do you have difficulty with grasping and use of small objects such as keys or pens?**
- No difficulty
- Mild difficulty
- Moderate difficulty

- Severe difficulty
- Very severe difficulty

Part II - Functional Severity Scale (SSS)

On a typical day during the past two weeks have hand and wrist symptoms caused you to have any difficulty doing the activities listed below? Please circle one number that best describes your ability to do the activity.

ACTIVITY	No Difficulty	Mild Difficulty	Moderate Difficulty	Severe Difficulty	Cannot do at all due to hand or wrist symptoms
Writing	1	2	3	4	5
Buttoning clothes	1	2	3	4	5
Holding a book while reading	1	2	3	4	5
Gripping a phone	1	2	3	4	5
Opening a jar	1	2	3	4	5
Household chores	1	2	3	4	5
Carrying grocery bags	1	2	3	4	5
Bathing and dressing	1	2	3	4	5

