2.2. Schedule of Events (SOE)

Schedule of Events Table – Active Device Group

Wks Into Study	Treatment Period (8wk)					Post-Treatment Period (12wk)					
	0	2	4	6	8	10	12	14	16	18	20
Enrollment ¹	X*										
NCS ²	X*										
BCTQ ³	X*	X*	X*	X*	X*		X*		X		X
Follow-up ⁴		X*	X*	X*	X*		X*		X		X
Usage Diary ⁵		X*	X*	X*	X*						
User Survey ⁶					X*						
Day	0	14	28	42	56	70	84	98	112	126	140

Schedule of Events Table – Sham Device Group

[figure not shown]
Wks Into Study	Treatment Period (8wk with Sham Device)					Post-Rx Period	Treatment Period (8 wk with Active Device)				
	0	2	4	6	8		10	12	14	16	18
Enrollment ¹	X*										
NCS ²	X*										
BCTQ ³	X*	X*	X*	X*	X*		X*	X	X	X	X
Follow-up ⁴		X*	X*	X*	X*		X*	X	X	X	X
Usage Diary ⁵		X*	X*	X*	X*			X	X	X	X
User Survey ⁶					X*						X
Day	0	14	28	42	56	70	84	98	112	126	140

* = required

- 1 - Enrollment includes completing ICF and baseline questions (eligibility check, CTS diagnosis/history, randomization, demographics, medical history)
- 2 - NCS within 24 months required to enroll
- 3 - BCTQ incorporated into Follow-up Surveys
- 4 - Follow-up Surveys completed by patient online
- 5 - Usage Diary completed online by patient DAILY
- 6 - User Feedback Survey (feedback on design and use of device) completed by patient online.

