6.1. Inclusion Criteria

1. Ages 21-65
2. Clinically diagnosed with mild to severe carpal tunnel syndrome (CTS)
3. CTS diagnosis confirmed by a nerve conduction study (NCS) performed within the past 24 months OR at enrollment/baseline visit
 - a. CTS severity determined via AANEM criteria¹³
 - b. Bilateral CTS accepted (worse wrist via NCS and/or BCTQ is designated as the study wrist)

4. BCTQ SSS ≥ 2
5. Reliable access to and ability to use Internet, Wi-Fi, or mobile data through computers, mobile devices, laptops, and/or tablets
6. Willing to abstain from any other treatment or therapies for CTS throughout the study
7. Ability to read and write English, or has a reliable person to assist with reading and writing English

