7.2. Enrollment, Baseline Assessment, and Randomization

7.2.1. Enrollment Procedures

After the subject has passed the pre-screening questionnaire, the subject will begin enrollment, which includes reading and signing the ICF/HIPAA Authorization, completing the Enrollment Form which includes the BCTQ and NPRS, and confirmation of CTS diagnosis via NCS. After confirming meeting all inclusion/exclusion criteria, the subject is considered enrolled. The subject will be randomized into either the active device group or the sham group and assigned a Subject ID.

Once the subject is enrolled, study devices are shipped (expedited) to the subject to begin treatment as soon after enrollment as possible. If a subject is bilateral, only the worse wrist (via NCS severity and/or SSS score) will be treated during the study. If NCS severity and/or SSS score are the same for both wrists, the dominant wrist will be treated. Standardized training and instructional materials will be provided to the subject on how to use the study devices, how and when to complete surveys, Diaries, etc.; how and when to report AE's/SAE's; and how to contact site staff or PI.

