7.2.3. Baseline Assessment

The Enrollment CRF captures Baseline assessment measures. These include:

- Date of birth/age
- Gender
- CTS severity (mild, moderate, or severe, from NCS)
- CTS diagnosis by hand (unilateral/bilateral, right/left/both)
- BCTQ and NPRS for affected hand(s)

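### For bilateral subjects, the treated-wrist rule and the BCTQ rating rule can point to different wrists, and no section says which wrist's SSS is analysed

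*Combined protocol and SAP*

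**What the plan says.** Three places deal with the wrist of a bilateral subject.

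- Section 6.1 (Inclusion Criteria): "worse wrist via NCS and/or BCTQ is designated as the study wrist".
- Section 7.2.1 (Enrollment Procedures): "If a subject is bilateral, only the worse wrist (via NCS severity and/or SSS score) will be treated during the study". It adds: "If NCS severity and/or SSS score are the same for both wrists, the dominant wrist will be treated". Neither section gives an order for the case where NCS and SSS disagree.
- Appendix I (the BCTQ form): a bilateral subject should "answer for the wrist that is more severe based on the nerve conduction study (NCS) results". The fallback is: "If difficult to tell, answer for your dominant hand". SSS plays no part in this rule, and the study or treated wrist is not mentioned.

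Other sections do not close the gap. Section 7.2.3 lists a baseline BCTQ for the affected hand or hands, which suggests two scores in a bilateral subject. For follow-up, the Schedule of Events says only: "BCTQ incorporated into Follow-up Surveys". On training, Section 11.1 says: "Subjects will be trained during or after enrollment on how to use and fill out these surveys"; it does not name the wrist to rate. The endpoint definitions (Section 4), the analysis population (10.4) and the analyses (10.5) refer to SSS without naming a wrist.

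**The concern.** SSS is the outcome for the primary paired comparison and for the secondary active-versus-sham comparison. Only one wrist wears a device. If the instruction on the form sends a bilateral subject to the other wrist, the score does not measure the treated wrist. If baseline is scored on one wrist and week 8 on the other, the paired change compares two different wrists.

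Bilateral subjects are eligible without a cap. NCS severity has three grades, so ties between wrists can occur. A tie is where SSS could select the treated wrist while the form sends the subject to the dominant hand. Only bilateral subjects can be affected, so any mis-scoring would also cloud the exploratory unilateral-versus-bilateral comparison that the pilot prompted.

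**Working it through.** **1. The plan's own figure.** Section 10.2 gives a difference of 0.4, SD 0.7, one-sided 0.05, power 0.8 and 25% attrition. With the normal approximation, n = 2 × (1.645 + 0.842)² × 0.7² / 0.4² = 37.9, so 38 per arm; 38 / 0.75 = 50.7, so 51 per arm and 102 in total. This matches the plan. With 38 completers per arm the exact one-sided t-test has power 0.795, which is the reference below.

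**2. Where the two rules differ.** Let D be the dominant wrist and N the non-dominant one. Each of NCS and SSS can be worse on D, tied, or worse on N, which gives 3 × 3 = 9 patterns. The Appendix I rule is taken as: NCS decides, and a tie goes to D.

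| Reading of the treated-wrist rule | Patterns (NCS, SSS) where treated and rated wrist differ | Count |
|---|---|---|
| NCS alone, tie to D | none | 0 |
| NCS first, SSS breaks ties | (tie, N) | 1 |
| SSS first, NCS breaks ties | (D, N), (tie, N), (N, D) | 3 |
| D if either measure ties; NCS settles disagreement | (N, tie) | 1 |
| D if either measure ties; SSS settles disagreement | (D, N), (N, D), (N, tie) | 3 |

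These count patterns; they are not frequencies. The reading with no conflict leaves SSS no role in choosing the wrist, although both sections name it.

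**3. Which data-collection format turns this into mis-scoring.**
- *Appendix I as printed at every visit:* one wrist is scored, SSS cannot choose between wrists, and selection falls back on NCS and dominance. The mismatch largely disappears.
- *Both wrists scored at every visit:* the treated wrist's SSS always exists. Only a statement of which score is analysed is missing.
- *Per-hand at baseline, Appendix I wording at follow-up:* SSS can select one wrist and the form can send the subject to the other. This is the harmful combination. The documents neither state it nor exclude it.

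**4. Illustration for the between-group test.** Assume a bilateral share b, a share m of those rated on the untreated wrist throughout, and a fraction f of the device effect lost on that wrist. Then effect = 0.4 × (1 − f·b·m), with 38 per arm, SD 0.7 and one-sided 0.05. None of b, m and f is in the documents.

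| b | m | Affected per 38 (38·b·m) | Effect, power (f = 1) | Effect, power (f = 0.5) |
|---|---|---|---|---|
| 0 | 0 | 0 | 0.400, 0.795 | 0.400, 0.795 |
| 0.3 | 0.1 | 1.1 | 0.388, 0.773 | 0.394, 0.784 |
| 0.5 | 0.2 | 3.8 | 0.360, 0.718 | 0.380, 0.758 |
| 0.6 | 0.3 | 6.8 | 0.328, 0.648 | 0.364, 0.726 |

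This assumes that bilateral subjects respond as fully as unilateral ones. If they respond little, as the unpowered pilot comparison in Section 5.2 hinted, there is less effect to dilute. No power figure is given for the primary paired test, because Section 3.3.2 allows for symptom improvement without the active mechanism.

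**5. Illustration for mixed wrists.** Take baseline on the study wrist and follow-up on the other. The shift in the active arm's mean improvement is b·m·(g − d). Here g is the baseline SSS gap, study wrist minus other (assumed 0 to 0.5), and d is the response shortfall of the untreated wrist (assumed 0 to 0.4). At b·m = 0.6 × 0.3 = 0.18 the limits are 0.18 × (0 − 0.4) = −0.072 and 0.18 × (0.5 − 0) = +0.090. At b·m = 0 the shift is 0. In the pattern (N, tie) the baseline scores are equal, so g = 0 and the shift cannot be upward.

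**The case against.** The strongest reply is that harm needs two BCTQ formats in one trial, per-hand at baseline and single-wrist at follow-up, and no section states that combination. The fielded surveys, the Enrollment Form and the training materials are not in the file. The Revision History says that the patient-reported forms were moved to separate documents, and those may name the treated wrist. Section 6.1 also uses the term study wrist, which most naturally means the wrist being evaluated. The bilateral and mis-rating shares are assumptions, and the low end of the power range needs all the unfavourable values at once.

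Most of this stands. It rules out two stronger conclusions that a reader might draw. One is that the rules flatly contradict each other: they agree whenever NCS and SSS point to the same wrist, and in all nine patterns if NCS alone decides. The other is that bilateral subjects were in fact scored on the wrong wrist, or that the results are biased in a known direction. The documents do not show the forms used, and the shift in step 5 can go either way.

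The reply does not remove the gap in the text. The version 1.1 revision that moved the other forms out also added the BCTQ as Appendix I, so that wording is the protocol's own and is still current. The term study wrist is not carried into the survey instruction, the endpoints or the analysis. If the fielded survey already names the wrist, the protocol still has to match it.

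**Conclusion.** The point holds as an internal inconsistency that should be fixed. Sections 6.1 and 7.2.1 and Appendix I can point to different wrists in 1 or 3 of 9 patterns on every reading except NCS alone, and the analysed SSS is not tied to the treated wrist. The gap in wording is certain; its effect on the data is not.

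Mis-scoring depends on per-hand SSS at baseline together with Appendix I wording at follow-up. The number of subjects affected is unknown and may be zero. Under the assumed shares, between-group power lies between 0.795 (no loss) and 0.65 with no device effect on the rated wrist, or 0.73 with half the effect. In the mixed-wrist case of step 5, the active-arm mean improvement moves by about −0.07 to +0.09 SSS points at most. These are sensitivity ranges, not estimates.

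**What to change.** - Reconcile Sections 6.1 and 7.2.1 and Appendix I into one ordered wrist-selection rule. The order is for the sponsor to settle.
- Record one study wrist (right or left) for each subject in the EDC before randomization.
- Replace the parenthetical in Appendix I with an instruction to answer for that recorded study wrist at every timepoint, and check that the fielded surveys match.
- State in Section 10.5 that baseline and follow-up SSS are both that wrist's scores.

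The cost is one survey line, one EDC field and aligned wording. No visits or subjects are added.
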